4.1.3 Lifestyle Considerations

The participants are free to engage in activities as usual while participating in this clinical trial. However, we request that they not share how to conduct the infant massage.

4.1.4 Strategies for Recruitment

4.1.4.1 Waiver of Authorization and Letter

Using a Waiver of Authorization and site permission to identify potentially eligible women through the Electronic Health Records systems of the recruitment sites (TMC and BUMC), potential participants are approached by clinic staff during their prenatal visits at the recruitment sites. If agreeable, the Recruiter introduces the study. When an eligible woman is interested, the Recruiter invites her to complete a 10-item ACE survey to assess level of childhood adversity. During a pandemic, many pregnant women receive care through telehealth visits rather than in-person visits. The research team member pre-screens using an eligibility checklist and then mails potentially eligible pregnant women a letter introducing the study. The content of the letter is dictated by the sites.

4.1.4.2 Recruitment Materials in Prenatal Clinics

After having obtained appropriate approvals, recruitment materials are placed in those clinics providing face-to-face visits. See Appendix B for examples of the Recruitment Materials. For providers or their delegates asking patients if they would be willing to discuss the study with our research team, we obtain the contact information, prescreen, and call the interested potential participants. A telephone script is followed by research personnel to describe the study and confirm eligibility including completing the 10-item ACE survey. If the woman scores ≥ 2 on the ACE and meets the other inclusion/exclusion criteria including expressing interest in reviewing the consent form, we will mail or email (their choice) an informed consent to review. The consent form indicates that we will use the results of the ACE instrument in the study. We call again to answer any study questions and ask if they are interested in participating. If they are agreeable, we consent in REDCap. Women are scheduled for a baseline data collection study visit in pregnancy where they continue the consent process to ensure they have understood the requirements of participation.

4.1.4.3 Referrals, Prenatal Classes, and Community Organizations

We network with other research studies recruiting from OB/GYN which refer patients who have given permission to be contacted by other research studies. Additionally, we recruit via community organizations such those offering prenatal classes. We present a one-minute description of the study and provide our study contact information on a power point slide. See Appendix B for Recruitment Materials.

4.1.5 Screen Failures

If a mother scores less than 2 on the ACE, we will remove all 13 elements of identification and retain only the ACE score without the corresponding answers to the 10 questions. We would like to determine if the inclusion/exclusion criteria such as the requirement to have access to a cell phone, screens out any portion of the population with high ACE scores. Additionally, this study has a second level of screening which occurs at the birth of the baby. If a participant delivers a baby not meeting the inclusion criteria such as full term (37 weeks 0/7 days) and healthy, they are withdrawn from the study and are not randomized. A minimal set of screen failure information is required to ensure transparent reporting of screen failure participants, to meet the Consolidated Standards of Reporting Trials (CONSORT) publishing requirements and to respond to queries from regulatory authorities. Minimal information includes demography, screen failure details, eligibility criteria, and any serious adverse event (SAE) which are retained with study records. Because there are no modifiable factors associated with screen failure, we do not rescreen participants.

4.1.6 Strategies for Retention

We expect an 80% retention rate. [REDACTED] previous R01 studies demonstrated 85% retention with women administering ATVV to their newborn preterm infant after hospital discharge for 2-months and demonstrated 72% retention for 2-3 months in another study. In this proposal, considering 20% attrition and collecting data through 3-postnatal months, we expect to acquire complete data in 24 months; thus, we require enrolling 3-4 women per week and retaining 2-3 women per week.

4.1.6.1 Track Enrollment and Retention Rates

As part of our quality control process, we monitor with monthly excel graphs our targeted versus actual enrollment and retention rates. We meet each week to review these two graphs and then discuss whether we should continue forward with the plan, discuss how to tweak the current course, or set a new course of action.

4.1.6.2 Establish Relationships

To maintain a culturally sensitive research team in this study, we hired Latinx (bilingual English and Spanish) team members. Additionally, our overall approach to enhance retention is to frequently reach out to mothers to develop a strong trusting relationship that reinforces how valuable their time is and how much we appreciate their participation. We will send holiday and birthday cards, and in addition to the automatic, daily, push-out texts we will send personal texts. We've learned that mothers prefer phone or text communication versus email or mail.

4.1.6.3 Participant Guidance Materials

We combine what we learned between our feasibility pilot and the RCT studies that Co-I [name] has conducted with preterm infants. We provide mothers with large colorful magnets which map out the study visits and expectations associated with participating in the study. See Appendix A. Additionally, we have appointment cards to provide to the mothers when we visit them in the hospital after birth of their baby. These appointments cards are used for all 3 post-natal visits.

4.1.6.4 Reminder Calls, Multiple Contact Numbers, and Flexible Scheduling

Staff send a text message and/or call one week before, two days before, and the day of a scheduled study visit for confirmation. When a participant cannot be reached for one week at the last known phone number, previously provided contacts are asked for assistance in locating her. Flexible scheduling of appointments and rescheduling if necessary, will accommodate mothers' schedules. At each monthly study visit, we will provide positive uplifting feedback to mothers in both groups on their experience with either ATVV and/or maternal caregiving in general.

4.1.6.5 Compensation

Mothers will be provided compensation for their time totaling \$300: \$50 at enrollment, \$50 at birth, \$50 at T1, \$50 at T2, and \$100 at T3. There is no compensation for the phone call at 6 months. Additionally, transportation fees are compensated at \$4 per visit or if the participant is traveling via their own vehicle, the College of Nursing maintains a reserved parking spot for research participants.

4.2 ATVV Intervention

4.2.1 Description of ATVV Intervention

The ATVV (Auditory, Tactile, Visual, Vestibular stimulation) is a 15 minute multisensory behavioral intervention consisting of infant-directed affectionate "motherese" speech, moderate touch massage, eye to eye gaze, and horizontal rocking.^(24, 76, 77) The ATVV intervention provides clinicians a low-cost, easily accessible intervention for mothers to implement that has been well researched by our team with preterm infants.⁽²⁵⁻³⁰⁾ The Pathways Foundation, whose educational materials are approved by the American Academy of Pediatrics, includes ATVV in their education for parents with preterm infants (<https://pathways.org/growth-development/massage-30-10-5/>). ATVV is an enjoyable daily opportunity for mothers to practice modeling M-I synchrony by using eye to eye gaze, affectionate speech and soothing touch.

During the 15-minutes in which ATVV is administered, multisensory stimuli are presented in gradual progression:^(24, 76, 77) "motherese" speech which is infant-directed speech typically high-pitched with a sing-song rhythm for 30 seconds, followed by massage for 10 minutes, with eye to eye gaze added as the infant becomes alert (ideally at the beginning of the intervention), and ending with rocking for the remaining 5 minutes. Importantly, "motherese" is maintained throughout the entire 15-minute intervention as long as disengagement cues are not exhibited. M-I engagement is attempted throughout the intervention; thus, mothers learn to identify, interpret and adapt to their infant's developmentally appropriate cues. The ATVV is applicable throughout the study period because it can be given even if the infant is too young for eye to eye gaze. Regardless of whether the infant is 1, 6, or 12 weeks old, ATVV is always offered contingent on infant cues to promote self-regulation and is withdrawn if the infant exhibits persistent disengagement cues.^(24, 76)

4.2.2 Administration of Intervention

ATVV is administered by mothers soon after birth,^(29, 30, 78) thus, filling a gap for simple interventions to promote engagement between mother and infant in early infancy when experience-dependent neural plasticity is high in maternal and infant brains.^(22, 23) In administering ATVV, mothers learn to be comfortable recognizing and adapting their behavior when the infant is signaling cues to engage or disengage. ATVV is an enjoyable daily opportunity for mothers to practice modeling M-I synchrony by using eye to eye gaze, affectionate “motherese” speech and soothing touch.⁽⁷⁸⁾

Mothers will be instructed to administer ATVV for 3 months, once daily at any time of their choosing, as long as it is in-between feedings when the infant is ready to interact but not too hungry (resulting in fussiness) and not too full (resulting in sleepiness). Daily use allows for ATVV to frequently reinforce positive M-I interaction. While twice versus once daily (in comparison to controls) yields more significant improvements in biologically at-risk preterm infants,^(23, 27, 29, 30) our pilot showed that once versus twice daily is more acceptable for mothers of healthy full-term infants. A research team member will teach the intervention with the assistance of the ATVV Intervention Manual for Parents, and the online ATVV teaching video targeting newborns. The ATVV is easily learned within one hour and shown to be highly acceptable by mothers in the literature and in our pilot (> 90% agreement with the ATVV Reliability Checklist).⁽⁹⁷⁾ In addition to taking home the ATVV manual, mothers can access our online teaching videos with infants at three different ages (newly born, 6 weeks, and 3 months old).

4.2.3 Concomitant Activities

We will not mention the use of oils or other massage techniques during instruction. If we are asked about their use during the weekly phone calls, we will discourage their use. Additionally, a breastfeeding guide is included in the hospital materials, but questions regarding breastfeeding are referred to their primary care provider or other resources.

4.3 Intervention Compliance

To monitor mothers' fidelity and dosage of ATVV once daily, we will use text messaging through Twilio, an electronic communications platform within REDCap. To have access to a phone capable of text messaging is an inclusion criterion to participate in the study. Participants may tire of responding to daily texts, but our daily text is extremely brief requiring only a keystroke to respond. If a phone becomes lost, we will provide a temporary one. Each evening, Twilio will text the following-

- Please tell us how many minutes you gave your baby the Massage Plus today. Choose between 0-15 minutes.
- Please tell us the level of stress you may have experienced today on a scale of 0-10.

The question on stress is included because the attention-control mothers also receive the identical text message and stress is a covariate. See section 4.5. We will monitor REDCap daily, and call mothers if we identify noncompliance two days in a row. Second, we will ask during the weekly phone calls if anyone else besides the mother gave the massage. At each weekly phone call and monthly study visit, we will review how often mothers use the intervention (self-report vs REDCap data) and discuss solutions to barriers of fidelity (e.g. lack of time, fussy or sleepy infant). We will also discuss who else may be giving the massage to their baby.

4.4 Attention-Control Comparison

4.4.1 Description of Attention-Control Group.

The Attention Control group is designed to provide a similar amount of research staff attention while in the hospital after birth, during weekly phone calls, and at 3 postnatal study visits but with the focus on didactic education (content distinctly different from the intervention). The Attention Control education protocol has been used for over 15 years in three of our previous RCTs, demonstrating acceptability to mothers, easy implementation, and rigor in isolating the impact of ATVV.^(28-30, 78) In our Attention Control, mothers will receive education on safe infant care including content on diapers, infant clothing, blankets, bathing, sleep positions, sleep habits, holding the baby, safety of infant equipment, breastfeeding, formula, and age-appropriate toys. The research member will use a prepared script and record in the Attention Control Record the information discussed. Since the ATVV intervention mothers will be contacted by a weekly phone call, the research member will also contact the Attention Control mothers by weekly calls to reinforce education. For both groups, weekly calls will include standard milestones in infant development.

4.4.2 Administration of Attention-Control Group.

The Attention-Control group is administered by the Research Assistant. An Attention-Control manual similar in appearance to the ATVV manual but differing in content is provided to mothers while they are in the hospital prior to discharge. Review of the infant care material while in the hospital is of equivalent time as required to instruct the ATVV Intervention group. The Attention-Control group also receives weekly phone calls to discuss topics of their request regarding infant care and development. We maintain focus on care and away from the mother-infant relationship. Questions regarding breastfeeding are referred to their primary care physician or other resources.

At the monthly visits and weekly phone calls with mothers in the attention control group, we will reinforce education on safe infant care (including content on diapers, infant clothing, blankets, infant care including bathing, sleep positions, sleep habits, holding the baby, safety of infant equipment, breastfeeding, formula, and age-appropriate toys). We will also include standard milestones in infant development for both groups.

4.4.3 Concomitant Activities

Equivalent to the ATVV Intervention group, we will not mention the use of oils or other massage techniques during instruction. If we are asked about their use during the weekly phone calls, we will discourage their use. A breastfeeding guide is included in the hospital manual (and provided to the ATVV Intervention group), but questions regarding breastfeeding are referred to their primary care provider or other resources.

4.5 Covariates

We will control for key covariates that may influence outcomes (Table 3). We include a range of instruments to assess psychosocial factors experienced as an adult that may impact the OXT system and parenting behavior.^(39, 110, 112, 128-130) To avoid an OXT spike during/after breastfeeding, we postpone blood draws to > 30-minutes after breastfeeding ends (a valid method used by us and others when studying OXT in breastfeeding mothers).⁽¹³¹⁾ Measuring M-I synchrony < 3 months of age has lower validity, thus we will use the Parenting Stress Index as a valid proxy for quality of parenting^(126,127) expecting it be associated with synchrony.

Table 3. Covariates

Construct	Operational Measure	B /I	1	2	3
Covariates					
Demographics Characteristics	Maternal: health status, age; weight; birth events; return of menses; birth control; mental health history; drug/alcohol use; marital status & father's involvement; education level; income Infant: health status; age; gestational age at birth; infant feeding method; infant's caretakers;				
Maternal Adversity**	Adverse Childhood Experiences (ACE): well-established 10-items on verbal, physical, and sexual abuse; emotional and physical neglect; household challenges (e.g., substance abuse, mental illness, prison). 71% response rate & 93-99% response rate to individual questions. ⁽²⁾ Distribution of scores (N=248,934) ⁽³⁾ 0=38%, 1=24%, 2=13%, 3=9%, $\geq 4=16\%$. Stable over time: test-retest kappa = 0.6-0.7 ⁽¹⁰⁸⁾ Maternal ACE ≥ 2 associated with infant developmental delay (N=311, p<0.05). ⁽¹⁰⁹⁾				
	Adverse Adult Experiences: 8-item modified version of the 10-item ACE providing a similar measure of adversity in adults > 18 years and associated with mental health. ⁽¹¹²⁾				
Maternal Mental Health**	Post-traumatic stress disorder (PTSD): Mini International Neuropsychiatric interview (MINI) Module H, V. 7.0.2 for DSM 5, 2016: 7-items ⁽¹¹³⁾ Concordance between PTSD in MINI versus Structured Clinical Interview for DSM-III-R Patients: Inter-rater reliability kappa=0.78, sensitivity=0.85, specificity=0.96, test-retest kappa=0.73. ⁽¹¹⁴⁾				
	Depressive symptoms: Patient Health Questionnaire (PHQ-9): 9-items using DSM-IV depression criteria. ⁽¹¹⁵⁾ Scores range 0-27 ⁽¹¹⁵⁾ Diagnostic validity from 8 primary care & 7 obstetrical clinics. Scores > 5 mild symptoms. Scores > 10: 88% sensitivity & 88% specificity for Major Depressive Disorder (MDD). Cronbach's $\alpha=0.86$ & 0.89. Scores ≥ 10 : 7-14 increased odds of MDD diagnosis. ⁽¹¹⁶⁾				
	Anxiety: Generalized Anxiety Disorders (GAD-7): 7-items ⁽¹¹⁷⁾ Scores range 0-21 ⁽¹¹⁷⁾ > 5 mild, > 10 panic disorder, social anxiety & PTSD (66-89% sensitivity & 80-82% specificity). ⁽¹¹⁸⁾ $\alpha=0.89$ in pregnant and non-pregnant. ^(119, 120)				

Parenting Stress**	Parenting Stress Index (PSI-SF): 36-items ^(123,124) 3 domains: parental distress, parent-child dysfunctional interaction, & difficult child. Appropriate from 0 - 3 years. Associated with maternal intrusiveness & sensitivity (elements of synchrony). ⁽¹²⁵⁾ Test-retest=0.85, $\alpha=0.91$. ⁽¹²³⁾			
--------------------	---	--------------------------	--------------------------	--------------------------

*Baseline (B), In-hospital (I), and postnatal months T1, T2, T3; **Available in Spanish

4.6 Minimization of Bias

4.6.1 Randomization and Blinding

This is an RCT comparing data between the ATVV and Attention Control groups. Random assignment is centrally controlled by our statistician using a computer-generated list of random numbers (0=intervention and 1=control), balanced so that half the mother-infant (M-I) dyads are in the ATVV group. Block randomization is used to randomize participants into two groups of 125. The algorithm will consider blocks of size 2,4,6 and 8 and constrain the number of blocks of each size so that the total number of participants is 250. The block labels will be shuffled and assignments to the control and intervention groups will be evenly split at random within blocks. Additionally, to reduce allocation bias we will use sealed allocation and an audit trail. The database manager will create and retain a pdf version with time and date "seal" for the allocation sequence. The database manager will also encrypt/hide the contents of the cells containing the allocation. Allocation will be made by temporal sequence of 1) date and time of notification, then 2) date and time of birth. A specified member of the research team will input the date and time of birth of the infant to "unseal"/reveal the allocation. The date and time of unsealing provides an audit trail. The research team and PI are blinded to the allocation sequence. The educator of the ATVV Intervention group and the educator of the Attention Control group will not have access to the randomization files and will be notified of allocation at the time of initiation of scheduling the hospital visit.

4.6.2 Division of Responsibilities

The Attention Control Educator (██████████) teaches infant care to the Attention Control women before hospital discharge. Similarly, the ATVV Intervention Educator (██████████) teaches ATVV to the ATTV women before hospital discharge. Instruction for both group conditions take approximately 30 minutes. To prevent bias, only Attention Control Educators will work with the Attention Control group, and only ██████████ will work with the ATVV group. The Program Coordinator assists with baseline data collections as needed to maintain this division of responsibility. However, personnel management and participant-language needs necessitate some flexibility.

4.7 Power Analysis

Our final sample size at the 3-month endpoint is estimated to be at least 100 per treatment arm, after a projected 20% attrition from enrollment of 250 women. This sample size will achieve 80% power to detect as significant a 0.44 standard deviation difference in primary outcomes (M-I synchrony gaze and affect) between treatment arms assuming $\alpha=0.025$ and a 2-sided test. Similar interventions on a related outcome (maternal sensitivity), and preliminary data from members of our team (on OXT level), showed between group effect sizes ranging from 0.28 to 0.62. In addition, the standardized differences in M-I synchrony ranged between 0.12 and 0.7 comparing at-risk (i.e., premature infants, maternal depression) and normal comparison groups at 3 and 9 months, supporting our choice of 0.4 as a feasible and clinically meaningful effect size. For aim 2 we have 80% power to detect modest correlations of 0.22 and larger assuming a conservative $\alpha=0.01$.

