3.2 Aims

To meet these objectives, we have designed a 4-year, single-site, randomized, attention-controlled clinical trial with the following aims:

Aim 1: Evaluate the efficacy of daily ATVV over 3 postnatal months among mothers with childhood adversity.

We hypothesize that compared to the Attention Control group (n=125), mother-infant dyads in the ATVV group (n=125) will exhibit:

- H1: Higher oxytocin (OXT) function (i.e., decreased oxytocin receptor (OXTR) gene methylation at candidate sites, and increased OXTR mRNA, OXTR protein, and OXT in maternal plasma, and increased OXT in infant saliva) at 1, 2, and 3 postnatal months.
- H2: More synchronous eye-to-eye gaze [primary], positive affect [primary], speech, and touch at 3 postnatal months.

Aim 2: Identify molecular mechanisms in the OXT system underlying mother-infant synchrony (N=250).

- H1: We hypothesize that lower mother-infant synchrony will be associated with dampening of the OXT system, evidenced by increased OXTR methylation at candidate sites, and decreased OXTR mRNA, OXTR protein, and OXT in maternal plasma, and decreased OXT in infant saliva at 3-postnatal months.

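### The Aim 2 power statement (80% for a correlation of 0.22) gives neither N nor sidedness; at the 200 dyads expected, a two-sided 0.01 test has about 71% power

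*Combined protocol and SAP*

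**What the plan says.** Section 4.7 (Power Analysis) gives the expected 3-month sample as "estimated to be at least 100 per treatment arm, after a projected 20% attrition from enrollment of 250 women", which is 200 dyads in total. It powers the two primary outcomes on that sample at alpha 0.025 "and a 2-sided test". The Aim 2 sentence follows and claims "80% power to detect modest correlations of 0.22 and larger". It sets alpha at 0.01 and calls that level conservative, but gives no N and no sidedness.

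Section 3.2 (Aims) attaches 250 to Aim 2: "Identify molecular mechanisms in the OXT system underlying mother-infant synchrony (N=250"). Its hypothesis has a direction, namely that "lower mother-infant synchrony will be associated with dampening of the OXT system", and is set at 3 postnatal months. The schedule in 1.4 and Table 2 in 3.3 show synchrony recorded at 3 months only, and 4.8.1 confirms that the behavioural outcomes are measured once, at the endpoint.

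Section 4.8.2, which describes the Aim 2 analysis, gives no significance level and no sidedness. The only sidedness stated in the document is two-sided, in 4.7 and 4.8.1, both times for the primary outcomes.

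**The concern.** An association between synchrony and an oxytocin measure can only be estimated in dyads with a synchrony recording, so its sample is the one retained at 3 months. A reader who takes the 200 dyads and the two-sided convention from the same paragraph cannot recover the Aim 2 claim.

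The stake is how Aim 2 results are read. Under a two-sided test, the chance of missing a true correlation of 0.22 is about 29% (100 - 71), not the 20% that the plan implies. Because 4.8.2 does not repeat the 0.01 level, the analysis is also not tied to the level on which the power claim rests.

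**Working it through.** **Inputs**
- Correlation r = 0.22, power 80%, alpha 0.01: section 4.7, Aim 2 sentence.
- N at 3 months: 250 x 0.80 = 200, section 4.7.
- Sidedness: not stated for Aim 2, so both cases are computed.
- Normal quantiles: 2.576 (0.01 two-sided), 2.326 (0.01 one-sided), 0.842 (80% power).

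**Formulas (Fisher z)**
- Power = Phi(atanh(r) x sqrt(N - 3) - z_alpha)
- Required N = ((z_alpha + z_power) / atanh(r))^2 + 3
- Detectable r = tanh((z_alpha + z_power) / sqrt(N - 3))

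Here atanh(0.22) = 0.2237 and sqrt(197) = 14.036, with product 3.139.

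**Step 1: reproduce the plan's figure.** With N = 200 and one-sided 0.01:
- Power = Phi(3.139 - 2.326) = Phi(0.813) = 79.2%.
- Detectable r = tanh((2.326 + 0.842) / 14.036) = 0.222.
- Required N = 204.

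This matches the stated 80% and 0.22 to rounding.

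**Step 2: the same sample, two-sided 0.01.**
- Power = Phi(3.139 - 2.576) = Phi(0.563) = 71.3%.
- Detectable r = tanh((2.576 + 0.842) / 14.036) = 0.239.
- Required N = ((2.576 + 0.842) / 0.2237)^2 + 3 = 236.5, so 237.

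**Step 3: full enrolment, two-sided 0.01.** With N = 250, sqrt(247) = 15.716:
- Power = Phi(0.2237 x 15.716 - 2.576) = 82.6%.
- Detectable r = 0.214.

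A claim of at least 80% would be true here, but only with no attrition.

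| N | Test at 0.01 | Power at r = 0.22 | Detectable r at 80% |
|---|---|---|---|
| 200 | one-sided | 79.2% | 0.222 |
| 200 | two-sided | 71.3% | 0.239 |
| 250 | two-sided | 82.6% | 0.214 |

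**Step 4: robustness.**
- A bias-corrected Fisher z, a noncentral t calculation and a bivariate-normal simulation were also run. Together with the formula above they give 71.3 to 72.1% for N = 200 two-sided and 79.2 to 80.0% one-sided. The two-sided N for 80% power is 233 to 237.
- Rounding of 0.22 does not close the gap: at N = 200 two-sided, r = 0.215 gives 68.8% and r = 0.2249 gives 73.8%.
- Better retention helps only in part. Section 4.1.6 cites 85% retention in earlier work; 0.85 x 250 = 212.5, and N = 213 gives 74.7%. Reaching 237 needs 237/250 = 94.8% retention.

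**Step 5: is 200 the plan's own basis?** For Aim 1, with 100 per arm, a 0.44 SD difference and two-sided 0.025, power = Phi(0.44 x sqrt(50) - 2.241) = Phi(0.870) = 80.8%. The primary-outcome claim in the same paragraph therefore reproduces on 200 dyads and a two-sided test.

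**The case against.** The strongest reply is that the figure does reproduce at the plan's own 200 dyads if the 0.01 test is one-sided, and that the Aim 2 hypothesis is directional. Section 4.7 says two-sided only of the primary outcomes. This stands as far as it goes: a reader might infer a calculation error, and the documents do not prove one. But no one-sided test is declared in 4.7, 4.8 or 4.8.2. A directional hypothesis does not settle the matter either, because the second Aim 1 hypothesis (more synchrony under the intervention) is just as directional and its primary outcomes are tested two-sided. One-sided 0.01 corresponds to two-sided 0.02, barely stricter than the 0.025 used for the primary outcomes, so it fits poorly with the description of the level as conservative. These are inferences about intent.

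A second reply is that Aim 2 is not only a 3-month correlation: 4.8.2 models oxytocin trajectories with repeated-measures models, which can use dyads without 3-month data. That is right for those analyses, but not for associations with synchrony, which exists at one time point. Multiple imputation is planned in 4.8.1 for the Aim 1 intention-to-treat analysis. It is not stated for Aim 2, and it would not restore the information of 250 observed dyads.

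A reader might also infer that the 250 attached to Aim 2 is itself an error. It is better read as an enrolment figure, parallel to the 125 per arm in Aim 1, and 4.7 discloses the fall to 200. Nor do the documents say that null Aim 2 results will be taken as evidence of no association. Aim 2 is a non-primary, mechanistic aim, and its clustering part is described as hypothesis-generating.

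**Conclusion.** The Aim 2 power claim has no stated basis, and on the plan's expected 200 dyads with a two-sided 0.01 test it is not delivered. Power at 0.22 is about 71%, roughly 9 points short, and the detectable correlation is about 0.24. This rests on two assumptions: that the synchrony-oxytocin associations are analysed in the 200 dyads with 3-month data, and that the test is two-sided, as everywhere else the plan states it. If the test is one-sided, the number is sound and only the declaration is missing.

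A reader might infer that 80% power at 0.22 requires the full 250. It does not: about 237 suffice two-sided, and 250 gives 82.6%. The sample size and the primary-outcome power are unaffected. The shift from 0.22 to 0.24 is modest, but the figure should be right because Aim 2 findings will be judged against it.

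**What to change.** In 4.7, replace the Aim 2 sentence with: *With 200 dyads expected at 3 months, 80% power to detect correlations of 0.24 or larger, two-sided alpha 0.01 (about 71% for 0.22).* In 4.8.2, name the same two-sided 0.01 level for the tests of association between synchrony and the oxytocin measures. If a one-sided test was intended, declare it in 4.8.2 and give N = 200 and the one-sided level in 4.7; the present 0.22 can then stay.

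The change is to wording only. It needs no extra dyads and no new analysis; its cost is a slightly less favourable stated figure.
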